1.2.2 Pharmacokinetics

The PK of MEDI-565 was studied in mice and cynomolgus monkeys. Following single dose IV administration in mice and cynomolgus monkeys, serum concentrations of MEDI-565 declined with a rapid initial distribution/elimination phase followed by a slower terminal elimination phase. In CD-1 mice (using a CD3 PK assay), although the terminal phase $t_{1/2z}$ was 5 hours, the AUC_{0-4h} was approximately 90% of the AUC_{inf} , representing a significant decrease in serum concentrations of MEDI-565 by 4 hours postdose, and thus indicating that the elimination of MEDI-565 may be better reflected by the initial $t_{1/2\alpha}$ of 0.2 hours. In C57BL/6 mice (using a whole-molecule PK assay), the AUC_{0-1h} was approximately 90% of the value of the AUC_{inf} , representing a significant decrease in serum concentrations of MEDI-565 by 1 hour postdose. The $t_{1/2\alpha}$ was 0.12 hours in wild-type mice and 0.13 hours in mice transgenic for human CEA. In cynomolgus monkeys (using a CD3 PK assay), the AUC_{0-4h} was 90% of the value of AUC_{inf} , representing a significant decrease in serum concentrations of MEDI-565 by 4 hours postdose. The $t_{1/2\alpha}$ was 0.37 hour. The subcutaneous t_{max} was 6 to 7.3 hours and SC bioavailability was 73% to 82%.

A 3-compartment model was fit to serum MEDI-565 concentration versus time data in cynomolgus monkeys to estimate the PK parameters. Based on allometric scaling of PK parameters from cynomolgus monkeys, the predicted human clearance was 2068 mL/hr; the central volume was 2958 mL; the peripheral volume was 9485 mL and 1195 mL for compartments 2 and 3, respectively; and intercompartmental clearance was 187 mL/hr and 183 mL/hr for compartments 2 and 3, respectively. The lowest EC₂₀ value obtained from an in vitro tumor cell lysis assay in response to treatment with MEDI-565 was 0.097 ng/mL. This concentration was selected as the minimum anticipated biological effect level (MABEL). The maximum recommended starting dose (MRSDD) of MEDI-565 is 0.75 µg administered as a 3-hour IV infusion once daily for 5 consecutive days. Based on the nonclinical information, the target efficacious dose of MEDI-565 in cancer patients is 1.5 mg administered as a 3-hour IV infusion once daily for 5 consecutive days.

Following IV infusion in subjects enrolled in Cohorts 1 through 10, peak serum concentrations of MEDI-565 increased approximately dose-proportionally from 0.48 ng/mL at the 0.75 µg dose level to 321 ng/mL at the 3 mg dose level. MEDI-565 concentrations decreased rapidly after the end of infusion with a short terminal elimination half-life of 3 hours. At the highest dose tested to date (3 mg), mean C_{max} at the end of infusion was 321 ng/mL, which decreased to 2.7 ng/mL within 24 hours. There was no notable accumulation between doses within a cycle and the PK was similar across cycles for a given dose.

1.2.3 Toxicology

Formal in vivo toxicity studies of MEDI-565 were not performed given the lack of a suitable pharmacologically relevant animal model to assess toxicity. The nonclinical strategy for MEDI-565 to support selection of the first dose in human and the Phase 1 clinical study is based on data from detailed in vitro cytotoxicity studies, human peripheral T-cell cytokine release assays, T-cell activation and proliferation assays, and PK modeling in cynomolgus monkeys. This strategy was chosen because there is no pharmacologically relevant animal model for in vivo toxicity studies of MEDI-565. The human PK profile for MEDI-565 was predicted based on its PK parameters in cynomolgus monkeys. Data from these in vitro and in vivo studies were collectively used to estimate the MABEL of MEDI-565, and to select a starting dose for the Phase 1 clinical study.

Results from in vitro studies on human cells, using the most sensitive test systems and assay conditions, were utilized to identify the effective concentrations of MEDI-565 that induced 20% of the maximum effect (EC₂₀ values). T-cell mediated lysis of cancer cells was the most sensitive measure for determining MABEL. Based on these results, the MABEL of MEDI-565 was calculated to be 0.097 ng/mL. Additional in vitro studies demonstrated that the ability of MEDI-565 to induce cytokine release and T-cell proliferation required simultaneous engagement of both CD3 on T cells and CEA on target cells. Thus, the in vivo activation of T cells in the absence of expression of CEA on target cells is not likely. Results from a PK and bioavailability study in male cynomolgus monkeys demonstrated only treatment-related, reversible erythema and bruising at the administration site following IV injection. There were no changes in clinical observations, body weight, serum chemistry, hematology, coagulation, or urinalysis parameters. Results from a GLP-compliant tissue cross-reactivity study on a full panel of human tissues showed expected staining of epithelial cells, consistent with known tissue expression of CEA ([Hammarström, 1999](#)).

1.3 Rationale for Study Conduct

The antitumor activity of MEDI-565 has been investigated using both in vitro and in vivo models for CEA-expressing human tumor cell lines and human T cells and PBMCs, either in cell culture or reconstituted in vivo using immunocompromised murine models. MEDI-565 treatment demonstrated significant in vivo antitumor activity specific to CEA-expressing tumors following either daily IV or SC dosing for 5 days in murine models. The ability of MEDI-565 to inhibit the growth of established human tumors in murine models was dependent on the presence of transferred human T cells and required the expression of CEA on the tumor cells. In vitro studies of MEDI-565 demonstrated significant and specific tumor cell cytotoxicity after a minimum of 24 hours of co-culture of MEDI-565 with CEA-expressing human tumor cells and T cells. These nonclinical studies suggest that MEDI-565 has potential antitumor activity against CEA-expressing malignancies and support a study design in which MEDI-565 is administered by either IV or SC administration daily for 5 days per cycle to subjects with CEA-expressing malignancies.

Study MI-CP216 will evaluate the safety, tolerability, immunogenicity (IM), pharmacology (PK and biomarkers), and preliminary antitumor activity of MEDI-565 given by IV infusion over 3 hours per day for 5 consecutive days of a 28-day cycle in adult subjects who have refractory GI adenocarcinomas for which no standard or curative therapies are available. The

study will consist of an initial dose-escalation phase to determine the maximum tolerated dose (MTD) or optimum biologic dose (OBD). Approximately 39 to 54 subjects will be evaluated.

Once the dose-escalation phase has been completed and an MTD/OBD has been achieved an additional 60 subjects may be enrolled. This expansion may include 20 subjects with refractory pancreatic adenocarcinoma, 20 subjects with refractory colorectal cancer (CRC), and 20 subjects with refractory gastroesophageal cancer. These tumor types were chosen based on high prevalence of CEA expression, poor outcomes following standard therapy, and differing levels of T-cell infiltration in the absence of specific immunotherapy. Commencement of the dose-expansion phase and selection of any tumor types will be based on any previously observed signal of antitumor activity and the safety profile of MEDI-565 emerging from the dose-escalation phase. Other study endpoints include PK, IM, and biomarkers of MEDI-565.

1.4 Benefit-risk and Ethical Assessment

MEDI-565 may offer a benefit to subjects with CEA-expressing malignancies and who have failed standard therapies. Nonclinical data support the antitumor activity of MEDI-565 in a variety of tumor cell lines. Specifically, MEDI-565 showed potent in vitro activity against multiple cell lines that express CEA. Subjects with relapsed or refractory GI adenocarcinoma have no available therapies after their disease has progressed while on treatment with approved or standard of care chemotherapies. Therefore, MEDI-565 has the potential to address an unmet medical need.

MEDI-565 is human species-specific, interacting with human CEA-expressing cells and human CD3-expressing T cells, and not with commonly accepted animal model systems used for toxicology and pharmacology studies. Efforts to develop suitable surrogate animal models have not been successful. Therefore, no suitable pharmacologically relevant animal models exist for predicting human safety or estimating the starting dose in the first-time-in-human (FTIH) study with MEDI-565. For this reason, the starting dose for Protocol MI-CP216 was determined based on in vitro experiments (T-cell mediated cytotoxicity of CEA-expressing cells) conducted with MEDI-565 to determine the MABEL, in conjunction with PK data from cynomolgus monkeys administered MEDI-565. While there are currently no identified risks for MEDI-565, because of limited clinical experience with this product, potential risks, based on the nature of the molecule, the mechanism of action, and the safety profile of other molecules that may be relevant include hypersensitivity, central nervous system toxicity,

hepatotoxicity, infection/viral re-activation, immune-related reactions, reproductive toxicity, hematologic toxicity, and infusion-related reactions, including cytokine release syndrome.

Two of 5 subjects in Cohort 10 (3 mg) experienced hypoxia within several hours after completion of the Cycle 1, Day 1 infusion that met the protocol definition of DLT. Under previous versions of the protocol, the occurrence of dose-limiting hypoxia in two subjects in Cohort 10 (3 mg dose) would have indicated that the MTD has been exceeded at the 3 mg dose. However, available data suggest that the observed DLTs were reversible and potential future cases of hypoxia temporally associated with MEDI-565 administration should be manageable with the implementation of additional risk mitigation measures including prophylactic dexamethasone administration prior to MEDI-565 administration and additional blood pressure, heart rate, and pulse oximetry monitoring during and following administration of MEDI-565. Thus, under Amendment 4 of the protocol, dosing will re-start at the next previously lower dose of 1.5 mg (Cohort 11) with implementation of the additional risk mitigation measures outlined above for all new subjects. Provided no more than 1 out of 6 subjects experience DLTs in the preceding cohort, dose escalation will continue in sequential fashion and re-evaluate the 3-mg dose (Cohort 12), followed by 5 mg (Cohort 13), 7.5 mg (Cohort 14), and 10 mg (Cohort 15) doses.

Currently, there are no anticancer agents approved by the United States Food and Drug Administration (FDA) with a CD3 effector mechanism to comparatively assess the potential safety and tolerability of MEDI-565, although one such agent is approved in the EU. A monoclonal antibody directed against CD3, muromonab-CD3 (Orthoclone OKT3) is approved by the FDA for use in acute transplant rejection. The most frequent adverse events (AEs) associated with muromonab-CD3 use are symptoms related to cytokine release syndrome, associated most strongly with the first few doses, which range from self-limited flu-like symptoms to more severe shock-like reactions. Cardiorespiratory findings included dyspnea, chest pain, bronchospasm, tachypnea, cardiovascular collapse, hypotension and adult respiratory distress syndrome (ARDS). Central nervous system events include seizures, encephalopathy, cerebral edema and aseptic meningitis, some resulting in permanent impairment. Other serious and occasionally fatal hypersensitivity reactions include cardiovascular collapse, hypotension, shock, tachycardia, angioedema, bronchospasm, urticaria and pruritus ([Orthoclone OKT3 package insert, 2004](#)).

There is experience with at least one molecule which targets CEA as a mechanism of action.¹³¹I-labetuzumab is a radio-iodinated anti-CEA antibody that is in clinical development as a radioimmunotherapy treatment of metastatic CRC. The primary toxicities associated with

this molecule were related to reversible myelosuppression, likely related to radiation exposure, and have not involved off-target normal epithelial tissues where CEA might be expressed at low levels, or other unexpected toxicities ([Liersch et al, 2005](#)).

Potential risks based on the mechanism of action for MEDI-565 have also been identified from safety data reported from clinical studies with other BiTE or similar multifunctional antibodies that have a known or postulated mechanism of action similar to MEDI-565.

Catumaxomab (Removab[®]) is a monoclonal bispecific, trifunctional antibody, approved in the European Union in 2009 for the intraperitoneal treatment of patients with malignant ascites. The antibody binds tumor cell epithelial cell adhesion molecule (EpCAM) and also T cell CD3 antigen ([Burges et al, 2007](#)). In addition, the Fc region provides a functional binding site to FcR γ positive accessory immune cells. Adverse effects have been primarily related to cytokine release symptoms and both IL-6 and TNF α have been found elevated in the majority of treated patients. Fever, chills, nausea and vomiting were frequently reported, while systemic inflammatory response syndrome (SIRS) occurred in 0.8% of patients ([Removab[®] Assessment Report, 2009](#)). Catumaxomab has also been studied in a single-dose, Phase 1 trial of non-small cell lung cancer patients, where the dose-limiting toxicity (DLT) consisted of transient Grade 3 and 4 elevations of AST/ALT/GGT ([Sebastian et al, 2007](#)). Unlike catumaxomab, MEDI-565 does not possess any FcR γ binding sites.

Blinatumomab (MT103, previously known also as MEDI-538) is a BiTE with specificity for the B cell antigen CD19 and CD3, in clinical development for the treatment of acute lymphocytic leukemia (ALL) and non-Hodgkin lymphoma (NHL). The majority of AEs from a Phase 1 trial in subjects with ALL consisted of flu-like symptoms, transient leukopenia/lymphopenia, and transient elevation of LFTs during the initial days of treatment. Central nervous system (CNS) symptoms (disorientation, confusion, speech disorders, tremor and convulsions), Grades 2 and 3, have been observed in approximately 17% of lymphoma patients ([Nagorsen et al, 2009](#)).

MT110 is a BiTE with specificity for EpCAM and CD3 currently in development in the EU for use in solid tumors. EpCAM is expressed on most solid tumors of epithelial origin. In a Phase 1 trial, MT110 has been administered at doses of up to 24 micrograms/day by continuous IV infusion in cycles of 28 days. Common Grade 1 or 2 related events included pyrexia, nausea, vomiting, diarrhea, and fatigue. There was one Grade 3 event of diarrhea. Transient elevations in transaminases were observed at all dose cohorts, which resulted in DLT in 3 subjects. One subject had a DLT of elevated bilirubin ([Fiedler et al, 2010](#)). EpCAM is known to be expressed on the biliary tract epithelium.

The experience with other therapies with similar mechanisms of action indicates that there is no consistent type or pattern of toxicities that can be predicted based on available data. While T-cell activation has been observed with some CD3-targeting agents, it is not uniform. Elevation in liver enzymes with EpCAM-specific multifunctional agents may be due to specific expression on biliary tract epithelium and is not necessarily predictive of toxicity with MEDI-565.

Given the promising activity of MEDI-565 in nonclinical models, the lack of available curative or life-prolonging therapies for subjects with refractory disease, and the additional risk mitigation measures being implemented with Amendment 4 to address potential future cases of hypoxia temporally associated with MEDI-565 administration, treatment with MEDI-565 represents a reasonable risk in this population.

2 Study Objectives

2.1 Primary Objective

The primary objective of this study is to determine the MTD and/or OBD of MEDI-565 in adult subjects and evaluate the safety profile in adult subjects with advanced GI adenocarcinomas who have no available standard or curative treatments.

2.2 Secondary Objectives

The secondary objectives of this study are:

- 1) To describe the PK of MEDI-565
- 2) To determine the IM of MEDI-565
- 3) To evaluate the antitumor activity of MEDI-565

2.3 Exploratory Objectives

The exploratory objectives of this study are:

- 1) To evaluate protein, nucleic acid, and cellular biomarkers in blood for MEDI-565 treatment
- 2) To assess potential CNS-related events using the Mini-Mental State Examination (MMSE) and the Timed Get-Up and Go Test

- 3) To assess multiple aspects of the tumor and tumor microenvironment before and following MEDI-565 treatment which may include: CEA expression, markers of necrosis or apoptosis, and potential changes in the nature and number of tumor-infiltrating lymphocytes

3 Study Design

3.1 Overview of Study Design

This is a FTIH, dose-escalation and expansion Phase 1 study. The first part is a multicenter, open-label, single-arm, dose-escalation study of MEDI-565 to determine the MTD or OBD and evaluate the safety, tolerability, PK, IM, and antitumor activity of MEDI-565 in adult subjects who have GI adenocarcinomas for which no standard or curative treatments are available. The second part is a dose-expansion study at the MTD or OBD in subjects with refractory CRC, refractory pancreatic cancer, or refractory gastroesophageal cancer. Approximately 4 to 10 investigational sites throughout the United States of America (USA) will participate in this study.

Dose escalation began with single-subject cohorts (Cohorts 1 through 4; see [Figure 3.1-1](#) and [Table 4.5.2-1](#)) and continued with standard 3+3 dose-escalation cohorts from Cohort 5 through 10. Ten cohorts have been enrolled to date. The starting dose of 0.75 µg was chosen based on the EC₂₀ (effective concentration that induced 20% of the maximum effect) obtained using a sensitive in vitro tumor cell lysis assay (Section 1.2.3). The initial 4 cohorts were single-subject cohorts with approximately 200% increases in dose up to the fifth cohort. The first subject enrolled in Cohort 5 (initially a single-subject cohort) experienced treatment-related Grade 2 AEs of vomiting and infusion reaction, and 2 additional subjects were enrolled per the original protocol. One of these additional subjects in Cohort 5 experienced a treatment-related Grade 2 AE of abdominal pain, triggering implementation of standard 3+3 enrollment in Cohort 5 and for all subsequent cohorts. As described in previous versions of this protocol, the dose in Cohort 6 was increased by 100% from Cohort 5 (from 60 to 120 µg) rather than by 200%. Doses in cohorts 6 through 10 were increased by approximately 100% to 150% following the dose-escalation rules described in Section 4.5.4.2. Under Amendments 1-3 of the protocol, the occurrence of dose-limiting hypoxia in 2 subjects in Cohort 10 (3-mg dose), indicates that the MTD has been exceeded at the 3-mg dose. However, available data suggest that the observed DLTs were reversible and potential future cases of hypoxia temporally associated with MEDI-565 administration should be manageable with the implementation of additional risk mitigation measures including prophylactic dexamethasone

administration prior to MEDI-565 administration and additional blood pressure, heart rate, and pulse oximetry monitoring during and following administration of MEDI-565. To minimize risk to subjects, Amendment 4 of Study MI-CP216 will re-start dosing at the next previously lower dose of 1.5 mg (ie, 1 dose level below the level at which the hypoxia events were observed) with implementation of the additional risk mitigation measures outlined above for all new subjects. A dose of 1.5 mg was chosen to re-start the study because it was judged to be more conservative from a safety standpoint and consistent with standard practice to de-escalate one dose level below the dose level (ie, 3 mg) at which the DLTs of hypoxia were observed. Provided no more than 1 out of 6 subjects experience DLTs in the preceding cohort, dose escalation is planned to continue in sequential fashion and re-evaluate the 3 mg dose (Cohort 12) followed by 5 mg (Cohort 13), 7.5 mg (Cohort 14), and 10 mg (Cohort 15) doses.

MEDI-565 will be administered by IV infusion over 3 hours per day for 5 consecutive days (ie, Days 1 through 5) every 28 days (defined as 1 cycle). Subjects in the dose-escalation phase are considered evaluable if they receive at least 1 full cycle of MEDI-565 and complete the safety follow-up through the DLT evaluation period of 28 days after the first dose of MEDI-565, or experience any DLT as defined in Section 4.5.4.5. Subsequent cycles may be delayed for up to 7 days for management of some types of toxicity (Section 4.5.4.4) or to accommodate scheduling issues. Nonevaluable subjects, defined as any subject discontinued during the DLT evaluation period for reasons other than a DLT, will be replaced in the same dose cohort. No intra-subject dose escalation will be allowed.

Dose escalation will continue until the MTD or a maximum dose of 10 mg is reached. In the event that no DLTs are observed during dose escalation and significant antitumor activity is observed, the Sponsor may halt dose escalation prior to determining the MTD provided that PK, pharmacology, safety and preliminary antitumor activity data support the use of an OBD below the MTD. On determination of the MTD or OBD, additional subjects will be enrolled so that a total of 6 subjects receive the MTD/OBD during the dose-escalation phase.

Once the MTD or OBD is determined, a total of 60 additional subjects (20 each with refractory pancreatic adenocarcinoma, refractory CRC, or refractory gastroesophageal cancer) may be enrolled at MTD or OBD in a dose-expansion phase. Commencement of the dose-expansion phase and the selection of any tumor types will be based on any previously observed signal of antitumor activity and the safety profile of MEDI-565 emerging from the dose-escalation phase. Subjects in the dose-expansion phase will receive MEDI-565 at the MTD or OBD as a 3-hour IV infusion per day for 5 consecutive days every 28 days (defined

as 1 cycle). Subjects in the dose-expansion phase are considered evaluable for antitumor activity if they receive at least 2 full cycles of MEDI-565 or discontinue due to progressive disease or toxicity. Nonevaluable subjects in the dose-expansion phase will be replaced. All subjects who receive any amount of MEDI-565 will be considered evaluable for safety.

A study flow diagram is shown in [Figure 3.1-1](#).

[figure not shown]

Figure 3.1-1 Study Flow Diagram

CRC = colorectal cancer; MTD = maximum tolerated dose; OBD = optimum biologic dose

The endpoints to be measured in this study are described in Section 7.3.

Standard 3+3 design for study enrollment is shown in [Figure 3.1-2](#).

[figure not shown]

Figure 3.1-2 Standard 3+3 Flow Diagram

DLT = dose-limiting toxicity; MTD = maximum tolerated dose; OBD = optimum biologic dose

The diagram above shows the work flow of a standard “3+3” design. A dose-escalation trial enrolls a group of 3 subjects at dose level X. If no subject experiences a DLT, escalate to the next higher dose level, X+1. If 2 or more subjects experience a DLT, stop dose escalation. If 1 subject experiences a DLT, expand dose level X to a total of 6 evaluable subjects. If 1 of 6 experiences DLT, escalate to dose level X+1. If 2 or more of 6 experience DLT, stop dose escalation. If the study stops at dose level X, then the MTD is estimated as the prior dose level (X-1).

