4.2.4 Replacement of Subjects

In the dose-escalation phase, nonevaluable subjects, defined as any subject discontinued during the DLT evaluation period for reasons other than a DLT, will be replaced in the same dose cohort.

In the dose-expansion phase, subjects who do not complete at least 2 cycles of MEDI-565 for reasons other than disease progression or toxicity will be replaced.

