7.2 Analysis Populations

The Evaluable Population for DLT includes all subjects enrolled in the dose-escalation phase who received at least one full cycle of MEDI-565 and completed safety follow-up through the DLT evaluation period (defined in Section 4.5.4.5) or experience any DLT. The Evaluable Population for DLT will be used for the MTD evaluation.

The Safety Population includes all subjects who receive any investigational product.

The Per-Protocol Population will include all subjects who complete 2 cycles of treatment or discontinue treatment due to disease progression or toxicity.

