7.3.2.3 Efficacy Assessments

Assessments of antitumor activity of MEDI-565 include ORR, TTR, DR, TTP, PFS, and OS. RECIST guidelines (v1.1; [Eisenhauer et al, 2009](#)) will be used to determine tumor response.

Objective Response Rate

Objective response rate is defined as the proportion of subjects with confirmed CR or confirmed PR according to RECIST guidelines. Confirmed responses are those that persist on repeat imaging study ≥ 4 weeks after the initial documentation of response. The 95% confidence interval of ORR will be estimated using the exact probability method.

Time to Response

Time to response will be measured from the start of MEDI-565 administration to the first documentation of response (CR or PR) and will only be assessed in subjects who have achieved objective response.

Duration of Response

Duration of response will be defined as the duration from the first documentation of objective response to the first documented disease progression. The DR will be censored on the date of last tumor assessment documenting absence of disease progression for subjects who have no

documented progression prior to data cutoff, dropout, or the initiation of alternate anticancer treatment. Duration of response will only be evaluated for the subgroup of subjects with an objective response using the Kaplan-Meier method ([Kaplan and Meier, 1958](#)).

Time to Progression

Time to progression will be measured from the start of treatment with MEDI-565 until the documentation of disease progression. Disease progression is defined according to RECIST guidelines v1.1 ([Eisenhauer et al, 2009](#)). The TTP will be censored on the date of last tumor assessment documenting absence of tumor progression for subjects who have no documented progression prior to data cutoff, dropout, or the initiation of alternate anticancer treatment. Subjects having no tumor assessments after the start of treatment with MEDI-565 will have TTP censored on the first date of treatment with MEDI-565. The TTP will be evaluated using the Kaplan-Meier method ([Kaplan and Meier, 1958](#)).

Progression-free Survival

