7.5 Sample Size

As of Amendment 4, the number of subjects who may be enrolled ranges from approximately 99 to 114, depending upon how many subjects are required per cohort based on occurrence of DLTs. The protocol specifies the exact circumstances guiding the number of subjects enrolled per cohort.

For the dose-escalation phase as of Amendment 4, approximately 39 evaluable subjects will be required if DLTs do not occur, for a total of 15 cohorts. Of the 15 cohorts, Cohorts 1-4

each require a minimum of 1 subject. Cohorts 5-15 follow a 3+3 design and each requires a minimum of 3 subjects (see [Table 4.5.2-1](#)). Up to approximately 54 evaluable subjects (1 subject each in Cohorts 1 through 4, 3 subjects in Cohort 5 through 9, 5 subjects in Cohort 10, and up to 6 subjects each in Cohorts 11 through 15) will be required during the dose-escalation phase.

At the discretion of the sponsor, more subjects may be enrolled for situations which might prompt selection of an intermediate dose and nonevaluable subjects will be replaced in the same dose cohort as described in [Section 4.5.4.2](#).

[Table 7.5-1](#) provides the probability of dose escalation to the next higher lever for each underlying true DLT rate at the dose levels with 3+3 design. For example, for a common toxicity that occurs in 10% of subjects, there is a greater than 90% probability of escalating to the next higher dose level. Conversely, for a toxicity that occurs with a rate of 60%, the probability of escalating to the next higher dose level is less than 10%.

Table 7.5-1 True Underlying DLT Rate at a Given Dose Level

True underlying DLT rate	10%	20%	30%	40%	50%	60%	70%	80%	90%
Probability of escalating dose	0.91	0.71	0.49	0.31	0.17	0.08	0.03	0.009	0.001

For the dose-expansion phase, approximately 60 subjects (20 subjects each) will be entered into 3 disease arms: refractory CRC, refractory pancreatic adenocarcinoma, and refractory gastroesophageal cancer. An equal number of subjects in each arm will be treated to evaluate the antitumor activity profile of MEDI-565. This projected sample size was chosen to obtain a preliminary safety and antitumor activity profile. A total of 20 subjects will provide approximately 80% power for testing the following hypotheses at 1-sided significance level of 0.1.

- Null hypothesis: undesirable ORR rate = 5%
- Alternative hypothesis: desirable ORR rate = 20%

8 Direct Access to Source Documents

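### Expansion-arm ORR rests on an evaluable set that excludes and replaces most other early stoppers; this biases ORR upward, and the 10% error level is not guaranteed above about 11% nonevaluable

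*Protocol*

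**What the plan says.** Protocol Section 3.1 (and the Study Abstract) treats expansion subjects as "evaluable for antitumor activity if they receive at least 2 full cycles of MEDI-565 or discontinue due to progressive disease or toxicity", and adds: "Nonevaluable subjects in the dose-expansion phase will be replaced". Section 4.2.4 states the same rule from the other side: "subjects who do not complete at least 2 cycles of MEDI-565 for reasons other than disease progression or toxicity will be replaced". Section 7.2 builds the filter into an analysis set: "The Per-Protocol Population will include all subjects who complete 2 cycles of treatment or discontinue treatment due to disease progression or toxicity". The only set in Section 7.2 that holds every treated subject is the Safety Population.

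Section 7.3.2.3 does not say which set ORR uses: "Objective response rate is defined as the proportion of subjects with confirmed CR or confirmed PR according to RECIST guidelines". Section 7.5 sizes each arm: "A total of 20 subjects will provide approximately 80% power for testing the following hypotheses at 1-sided significance level of 0.1". The hypotheses, in percent, are "Null hypothesis: undesirable ORR rate = 5" and "Alternative hypothesis: desirable ORR rate = 20". No analysis set and no expected nonevaluable rate accompany them.

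**The concern.** Whether a subject counts as evaluable is settled after treatment starts, and the reasons that remove a subject are not neutral. Section 4.2.3 lists withdrawn consent, loss to follow-up, noncompliance and new anticancer therapy separately from progression and toxicity. It also tells sites to record a subject who refuses to come back as having withdrawn consent. It lets the investigator defer a diagnosis of progression to the next scheduled scan when inflammation is suspected. A patient who is getting worse and stops attending, or moves to another treatment before progression is documented, can therefore be replaced instead of being counted as a failure.

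Such a subject has very little chance of a confirmed response. The first scheduled on-treatment scan follows two 28-day cycles (Section 5.2.2.17), and a response must be confirmed at least 4 weeks after it is first seen (Sections 5.3.7 and 7.3.2.3). Losses of this kind are plausible: entry requires a life expectancy of only 3 months (Section 4.2.1), and two cycles take 56 days.

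At stake is the meaning of the reported ORR. The 5% and 20% benchmarks would be compared with a rate from which some treatment failures had been removed and their places refilled.

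**Working it through.** **Inputs.** From Section 7.5: n = 20 per arm, null ORR 5%, alternative 20%, one-sided level 0.10, power about 80%. From Sections 3.1, 4.2.4 and 7.2: the evaluability and replacement rule. Assumed, because the protocol is silent: a share d of treated subjects is nonevaluable, none of them responds, and the 5% null describes all treated subjects.

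**Step 1: the protocol's own figure.** Exact single-stage binomial, X ~ Bin(20, p).
- At least 3 of 20: P(X ≥ 3 | 0.05) = 0.0755 and P(X ≥ 3 | 0.20) = 0.794. This reproduces the stated power of about 80%.
- At least 2 of 20 gives a type I error of 0.264, above 0.10.
- At least 4 of 20 gives a power of 0.589.

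So the implied rule is at least 3 responses in 20. It spends 7.55% of the 10% allowed.

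**Step 2: effect of replacement.** If all responders lie in the evaluable share 1 - d, then evaluable ORR = all-treated ORR / (1 - d). With 20 evaluable places filled, type I error = P(X ≥ 3 | n = 20, p = 0.05/(1 - d)).

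| d | evaluable ORR when the all-treated ORR is 5% | relative inflation, 1/(1-d) - 1 | type I error, ≥3/20 |
|---|---|---|---|
| 0 | 5.0% | 0% | 0.0755 |
| 5% | 5.3% | 5% | 0.085 |
| 10% | 5.6% | 11% | 0.097 |
| 15% | 5.9% | 18% | 0.110 |
| 20% | 6.3% | 25% | 0.126 |
| 25% | 6.7% | 33% | 0.145 |

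The 0.10 limit is crossed at d of about 11.4%. Filling 20 evaluable places then takes 20/(1 - 0.114) ≈ 22.6 treated subjects, so 2 to 3 are replaced per arm.

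**Step 3: the same in whole subjects.** With N treated to fill 20 places, p = 0.05 × N/20. Two replaced (N = 22, p = 0.055) gives 0.094. Three replaced (N = 23, p = 0.0575) gives 0.104.

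**Step 4: effect on the estimate.** Three responders among 25 treated is 3/25 = 12.0% (exact 95% CI 2.5% to 31.2%). On the 20 evaluable it is 3/20 = 15.0% (3.2% to 37.9%).

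**Step 5: check of the remedy.** Putting everyone treated in the denominator does not restore the level if the cut-off stays at 3: with N = 24, P(X ≥ 3 | 0.05) = 0.116. The smallest cut-off that keeps type I error at or below 0.10 depends on N:

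| N treated | cut-off | type I error | power at 20% |
|---|---|---|---|
| 20 | ≥3 | 0.075 | 0.794 |
| 22 | ≥3 | 0.095 | 0.846 |
| 23 | ≥4 | 0.026 | 0.703 |
| 25 | ≥4 | 0.034 | 0.766 |
| 27 | ≥4 | 0.044 | 0.818 |

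**The case against.** The strongest reply is that the protocol nowhere says ORR is computed on the evaluable set. Section 7.3.2.3 speaks only of subjects, and Section 7.1 leaves endpoint details to the SAP, which is not shown. That is true, and exclusion from ORR is an inference. It is the natural one: the protocol calls these subjects not evaluable for antitumor activity, builds the same filter into the Per-Protocol Population, and sizes the test on 20 subjects whose places are refilled. The evaluability and replacement rules are fixed in the protocol itself.

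An End of Treatment scan is due whatever the reason for stopping, unless one was done in the preceding 14 days (Section 5.2.2.18), and disease follow-up continues for some subjects (Section 4.2.3). Some early stoppers may therefore have progression documented, and a confirmed response is not strictly impossible. This softens the assumption of no responders but does not reverse the direction of the bias.

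Several stronger readings are tempting and are not supported:
- **That the 10% error rate is broken.** It survives two replaced non-responders per arm. If the 5% null is meant for evaluable subjects, it holds at any replacement rate.
- **That deaths as such are excluded.** The rule does not mention death. A subject who stops for progression or toxicity and then dies stays evaluable; only a death attributed to neither falls outside.
- **That replacing ineligible subjects at any point in expansion (Section 4.2.3, item 3) deletes known outcomes.** That item adds a subject. It does not remove one from analysis, and the Per-Protocol definition has no eligibility condition.
- **That a go decision is biased.** No go rule is tied to this test. Section 3.4 says shrinkage in one or two subjects may justify further study and that the phase does not stand in for a randomised trial.

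**Conclusion.** The point holds in a conditional form. Following the stated rules, ORR on the evaluable set overstates ORR among all treated subjects by a factor of up to 1/(1 - d), reached when no nonevaluable subject responds. That is 11% in relative terms at d = 10% and 25% at d = 20%. The 10% type I error is not guaranteed once more than about 11% of an arm is nonevaluable, provided the 5% null refers to all treated subjects. At d = 15% and 20% the error is 11.0% and 12.6%: modest excesses. The value of d is an assumption throughout. ORR is a secondary endpoint and Section 7.5 calls the expansion profile preliminary, which limits the consequence. The correction is still worth making, because the bias runs in one direction and costs little to remove.

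**What to change.** In Sections 7.2 and 7.3.2.3, define the main ORR denominator in each expansion arm as all treated subjects, and count anyone without a confirmed response, including anyone who dies early, as a non-responder. Measurable disease is already required for entry to expansion (Section 4.2.1), so no further condition is needed. State that replaced subjects stay in this denominator. Report Per-Protocol ORR as a sensitivity analysis. In Section 7.5, say that the 5% and 20% rates refer to all treated subjects, and give the response cut-off for the number actually treated, for example at least 3 for N = 22 and at least 4 for N = 25, as in the second table under the working.

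The cost is wording in the protocol and, where one exists, the SAP. The reported ORR will be slightly lower, and at some N power falls below 80%: 70.3% at N = 23 and 76.6% at N = 25. The sponsor can accept this or plan for a treated N, such as 27, at which power is again above 80%.
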